## SCIENTIFIC BACKGROUND

Tinnitus, characterized by the perception of sound without external stimuli, affects a significant portion of the population and can lead to psychological distress and functional impairments. The prevalence of tinnitus increases with age, and it is often described as ringing, buzzing, or hissing sounds in one or both ears. Current treatments include medication and sound therapy, but there is a need for more effective interventions. Cognitive behavioral therapy (CBT) has been shown to be effective in managing tinnitus by addressing negative thoughts and behaviors associated with the condition.

CBT, originally developed by Beck in the 1950s, integrates cognitive therapy and behavioral techniques to manage conditions like depression and anxiety. It is based on the concept that unrealistic thoughts and negative beliefs lead to various negative emotions and behavioral impairments. By correcting these cognitive distortions through counseling and education, individuals can develop more positive and realistic thinking patterns, reducing negative emotions and behavioral issues. CBT has been widely used for conditions such as insomnia, chronic pain, and anxiety disorders, and its effectiveness in improving quality of life is well-documented.

In the context of tinnitus, CBT is particularly beneficial as it helps modify the patient's reaction to tinnitus, reducing its impact on daily life. Studies have consistently shown that CBT can significantly decrease tinnitus-related distress, improve emotional well-being, and enhance quality of life. For instance, research involving internet-based CBT has demonstrated comparable efficacy to traditional face-to-face CBT, offering a convenient and accessible treatment option for tinnitus sufferers.

Sound therapy is another approach used to alleviate tinnitus symptoms. It aims to reduce the contrast between tinnitus and silence, thereby decreasing the perception of tinnitus. Sound therapy can involve various types of sounds, such as white noise or nature sounds, and is often used in conjunction with CBT to enhance its effectiveness. Mobile apps have become increasingly popular for delivering sound therapy due to their accessibility and flexibility, allowing patients to customize their treatment based on personal preferences.

The integration of CBT and sound therapy into mobile apps offers a promising solution for managing tinnitus. These apps provide tailored interventions that can be accessed conveniently, making them an attractive option for individuals seeking to manage their tinnitus symptoms effectively. By leveraging the strengths of both CBT and sound therapy, such apps aim to improve the quality of life for tinnitus sufferers by reducing psychological and physical functional impairments associated with the condition.

## OBJECTIVES

The purpose of this study is to evaluate the efficacy and safety of CBT based digital therapeutics,

in reducing psychological and physical functional impairments caused by subjective tinnitus. This prospective, randomized, single-blind (participant), parallel-design, superiority, confirmatory trial aims to assess whether CBT and sound therapy software can effectively alleviate the distress associated with tinnitus by providing tailored CBT and sound therapy to patients.

## **DESIGN**

This study is designed as a prospective, multicenter, randomized, single-blind (participant), parallel-design, superiority, confirmatory trial. It aims to evaluate the efficacy and safety of a CBT based digital therapeutics, in reducing psychological and physical functional impairments caused by subjective tinnitus. Participants will be randomly assigned to either the intervention group using CBT based digital therapeutics or the control group receiving conventional CBT educational materials. The trial will assess changes in Tinnitus Handicap Inventory (THI) scores and other relevant outcomes over a period of 6 weeks.

## **METHODS**

Participants are selected based on criteria including being aged 19 or older, having chronic tinnitus for more than three months, a THI score between 18 and 77, and the ability to use internet and applications. Exclusion criteria include objective tinnitus, middle ear infections, and other psychiatric conditions. The intervention involves using CBT based digital therapeutics, while the control group receives conventional CBT educational materials. The trial evaluates changes in THI scores and other relevant outcomes over six weeks.

## **STATISTICAL ANALYSIS PLAN**

Statistical tests are conducted at a significance level of 5% or less, using two-sided tests. Descriptive statistics for continuous variables include mean, standard deviation, median, minimum, and maximum, while categorical variables are summarized by frequency and percentage. If data do not meet the assumption of normality, non-parametric methods like the Wilcoxon signed-rank test are used instead of parametric methods like the paired t-test, with normality assessed using the Shapiro-Wilk test, Kolmogorov-Smirnov test, or Q-Q plots. The latest version of R is used for statistical analysis, but other software can also be employed.

The analysis groups are defined as follows: the Full Analysis (FA) set includes all participants who have used the medical device at least once and undergone efficacy evaluation; the Per Protocol (PP) set consists of participants from the FA set who completed the trial without major protocol deviations; and the Safety Analysis Set includes all participants who have used the medical device at least once. Demographic information collected for the FA set includes age, height, weight, gender, smoking status, and alcohol consumption.

The primary efficacy variable is the change in Tinnitus Handicap Inventory (THI) total score from baseline to 6 weeks, analyzed using ANCOVA to compare groups while adjusting for baseline THI

and stratification factors. Secondary efficacy variables include changes in THI subscales, Tinnitus Functional Index (TFI), Visual Analog Scale (VAS) for negative emotions and thoughts, Beck Depression Inventory (BDI), and Beck Anxiety Inventory (BAI). Each secondary efficacy variable is analyzed using descriptive statistics at baseline and at 2, 4, and 6 weeks, with paired t-tests or Wilcoxon signed-rank tests used within groups and two-sample t-tests between groups. Repeated Measures ANOVA or linear mixed models can be used to assess changes over time.

Safety evaluation includes reporting adverse events, assessing vital signs using paired t-tests or Wilcoxon signed-rank tests, and analyzing physical and laboratory findings with paired t-tests for continuous variables and McNemar's test for categorical variables. Missing data are handled using the Last Observation Carried Forward (LOCF) method for the FA set, with available data used as is for other analyses.

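### Every analysis set requires use of the medical device, which is undefined for the control arm, and no all-randomised set exists, so the primary ANCOVA can lose randomised participants for post-randomisation reasons

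*Combined protocol and SAP*

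**What the plan says.** The Statistical Analysis Plan defines three sets and no others:

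- **Full Analysis:** "the Full Analysis (FA) set includes all participants who have used the medical device at least once and undergone efficacy evaluation".
- **Per Protocol:** "the Per Protocol (PP) set consists of participants from the FA set who completed the trial without major protocol deviations".
- **Safety:** "the Safety Analysis Set includes all participants who have used the medical device at least once".

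The Methods section describes the arms in one sentence: "The intervention involves using CBT based digital therapeutics, while the control group receives conventional CBT educational materials". The Design section likewise has "the control group receiving conventional CBT educational materials".

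The primary variable, change in THI total score from baseline to 6 weeks, is "analyzed using ANCOVA to compare groups while adjusting for baseline THI" and stratification factors. That sentence names no analysis set. On missing values the plan says: "Missing data are handled using the Last Observation Carried Forward (LOCF) method for the FA set".

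**The concern.** A set definition should tell a programmer, before any outcome is seen, which randomised participants are analysed. This one does so for the app arm only. For controls, someone must later decide whether being handed the materials, opening them or being presumed to have used them counts. Each choice gives a different FA set. The trial is described as a confirmatory superiority trial and only participants are stated to be blinded, so nothing shows that the decision would be made without knowledge of arm or data.

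The second problem remains even if the wording is repaired arm by arm. Whether a person starts the allocated intervention is known only after randomisation. If the share of non-starters differs between arms, and non-starters follow a different course, removing them means the ANCOVA no longer compares the groups that were randomised. The Safety set has the same undefined comparator, so the control denominator for adverse events is also unsettled.

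**Working it through.** **Step 1: apply the definitions as written.** The plan states no figure on this point, so the first check is of the text.

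| Set | Condition | App arm | Control arm |
|---|---|---|---|
| FA | device used at least once, and efficacy evaluation undergone | can be determined apart from the meaning of evaluation | no device supplied, so empty if read literally |
| PP | member of FA, no major deviation | follows FA | empty |
| Safety | device used at least once | can be determined | empty |

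An empty control arm contradicts the between-group ANCOVA in the same section, so some unwritten rule for controls must be intended.

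**Step 2: apply the generous reading.** Take the medical device to mean the allocated intervention. Three gaps remain:

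- Use of educational materials has no criterion.
- The efficacy evaluation is not said to be post-baseline. If it is, early dropouts leave the FA set before LOCF can act on them.
- LOCF works within the FA set, so it restores nobody who was excluded from it.

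Whichever set the ANCOVA uses, the device-use condition applies, because every defined set carries it.

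**Step 3: how large could the effect be?** All inputs here are assumptions: THI SD 15, baseline to week 6 correlation 0.6, 50 or 100 randomised per arm, and no true treatment effect. Let pA and pC be the shares excluded as non-users in the app and control arms, and let d be the number of THI points by which non-users improve less. Both arms contain the same underlying share, max(pA, pC), of such participants. Then

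bias = d × (pA − pC) / (1 − min(pA, pC)).

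For 20% vs 10% with d = 10: 10 × 0.10 / 0.90 = 1.11 points. For 20% vs 0%: 10 × 0.20 / 1 = 2.0 points.

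Type I error was obtained from 20,000 simulated null trials per scenario (ANCOVA of week 6 THI on arm and baseline, two-sided 5%). The Monte Carlo standard error is about 0.15 percentage points at 5% and 0.27 at 18%.

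| Excluded, app vs control | d | Bias (THI points) | Type I error, 50 per arm | 100 per arm |
|---|---|---|---|---|
| 10% vs 10%, or 20% vs 20% | 10 | 0 | 4.9% | 4.8% |
| 5% vs 0% | 10 | 0.5 | 5.5% | 6.0% |
| 10% vs 0% | 5 | 0.5 | 5.6% | 5.8% |
| 10% vs 5% | 10 | 0.5 | 5.4% | 5.8% |
| 10% vs 0% | 10 | 1.0 | 6.7% | 8.4% |
| 20% vs 10% | 10 | 1.1 | 6.7% | 9.0% |
| 20% vs 0% | 10 | 2.0 | 11.6% | 18.4% |
| 10% vs 20% | 10 | 1.1 against the app | 6.9% | 9.2% |

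**Hand check of the 20% vs 0% row, 50 per arm.** The residual SD is 15 × √(1 − 0.6²) = 12. The standard error is 12 × √(1/40 + 1/50) = 2.55. The shift is 2.0 / 2.55 = 0.79 standard errors. Type I error is Φ(−1.96 + 0.79) + Φ(−1.96 − 0.79), about 12%. This is slightly above the simulated 11.6% because it ignores the extra variance from non-users who remain in the control arm.

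**Step 4: a second formulation.** Suppose instead that excluded participants do worse than retained ones by g SD in both arms, with no effect among all randomised. The bias is then (pA − pC) × g SD. With g = 0.5 and 50 / 100 / 200 per arm, type I error is 5.7% / 6.4% / 7.8% for 10% vs 0%, and 7.6% / 10.2% / 15.6% for 20% vs 0%. The pattern is the same.

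**The case against.** The strongest reply is that the plan clearly means controls to be analysed, since it specifies between-group tests, so the literal reading is a slip of wording. The LOCF sentence also points to the FA set as the main efficacy set. A single use is a low bar, participants are blinded, and all must be able to use internet and applications, so non-starters may be few. The larger error rates require 20% of the app arm never to start, full uptake in control and a 10-point gap. The milder unequal scenarios give 5.4% to 6.0%.

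Much of this stands. The literal reading is a drafting error, FA is the likely intended set, and the bias may be negligible. None of it supplies the missing control criterion or an all-randomised set, and the membership gap exists even if non-use is zero.

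Two further points limit what the fix can promise:

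- If non-users also lack follow-up THI, an all-randomised set moves the problem into the missing-data method and does not abolish it. The simulation assumed week 6 THI was observed for everyone analysed, and its zero bias under equal non-use relies on the two arms having the same kind of non-user.
- Including non-users dilutes the estimate. If 20% of the app arm gained nothing, the effect would shrink to 0.8 of its size among users, and holding power would take about 1/0.8² = 1.56 times the participants. The dilution is slight if non-use is small. The plan states no power figure that this could breach, and the diluted effect is the randomised comparison.

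**Conclusion.** The concern holds, and the definitions must be corrected. From the text alone it is certain that all three sets rest on device use, that use has no meaning for controls, and that no set contains everyone randomised. As written, control membership of the confirmatory analysis and of the safety comparison cannot be determined.

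The consequence for the result is uncertain in both size and direction. In the scenarios of Step 3 it runs from no bias to 2.0 THI points and a type I error of 18.4%, and it can favour either arm. Those figures illustrate the risk under assumed inputs and are not estimates for this trial. The need for correction rests on the undefined membership and the post-randomisation exclusion, not on any one row of the table.

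**What to change.** - **FA set:** define it as all randomised participants, analysed in the assigned arm whether or not they used the app or the materials. Name it as the set for the primary ANCOVA.
- **No post-baseline THI:** state how these participants are handled, since LOCF has only the baseline value to carry forward for them. Suitable options are multiple imputation, or a likelihood-based mixed model of THI at baseline and weeks 2, 4 and 6 with baseline as an outcome, so that baseline-only participants stay in. The plan already summarises THI subscales at those weeks. Add a sensitivity analysis assuming no change from baseline for these participants.
- **Safety set:** define it as everyone who received the app or the educational materials, grouped by what they received.
- **Use at least once:** keep this condition only for a supplementary or Per Protocol set, with a stated and equivalent criterion in each arm, such as first log-in and first opening of the materials.

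**Cost:** rewording of the set definitions, one specified missing-data method and one sensitivity analysis. No visits are added, but follow-up THI should be sought from non-users too, which is a matter of trial conduct. The estimate will be diluted in proportion to non-use. The change should be made before outcome data are seen.

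### Secondary endpoints are compared between arms by unadjusted two-sample t-tests, although the primary ANCOVA adjusts for baseline and stratification factors, and the within-arm tests are not labelled descriptive

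*Combined protocol and SAP*

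**What the plan says.** All of this is in the section headed Statistical Analysis Plan.

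- **Primary variable.** The THI total change to week 6 is "analyzed using ANCOVA to compare groups while adjusting for baseline THI". The same model also takes in the strata used at randomisation, which the plan does not name.
- **Secondary variables.** They are defined as changes: "Secondary efficacy variables include changes in THI subscales, Tinnitus Functional Index (TFI"), with VAS, BDI and BAI completing the list.
- **Secondary summaries.** "Each secondary efficacy variable is analyzed using descriptive statistics at baseline and at 2, 4, and 6 weeks".
- **Secondary tests.** The same sentence then sets out the testing: "with paired t-tests or Wilcoxon signed-rank tests used within groups and two-sample t-tests between groups". No baseline or stratification term is given for the between-group test.
- **Longitudinal option.** "Repeated Measures ANOVA or linear mixed models can be used to assess changes over time". This is permissive, is aimed at the time course and names no covariates.
- **Level.** "Statistical tests are conducted at a significance level of 5% or less, using two-sided tests". The rule is general, so it covers the within-arm tests too. Nothing calls those tests descriptive; the word is used only for the summaries.

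**The concern.** A change score subtracts baseline, which fixes the slope of follow-up on baseline at 1. ANCOVA estimates that slope, and it is usually below 1. When it is, the t-test on change has a larger variance than necessary, and a chance baseline difference between arms carries over into the estimated effect. If randomisation was balanced within strata that predict outcome, leaving the strata out of the analysis also makes the t-test conservative.

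The plan accepts this reasoning for the THI total but not for the other scales, and gives no reason. The THI subscales are thus analysed by a different estimator from the total they make up. At stake are wider confidence intervals and lower power on every secondary comparison.

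The within-arm tests raise a separate, smaller matter. Both arms receive CBT content, so both may improve. Significance in one arm only is then easily misread as efficacy, although it says nothing direct about the difference between arms.

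**Working it through.** **Inputs.** The documents supply the two-sided 5% level, the two methods and the visits. They state no sample size, SD, correlation or power, so there is no planned figure to reproduce. Everything below is assumed: correlation ρ from 0.4 to 0.8, and SD ratio k = baseline SD / follow-up SD of 1, 0.9 or 0.8. Values below 1 are plausible for THI because entry requires "a THI score between 18 and 77" (Methods) while follow-up scores are not limited.

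**1. Precision.** With the follow-up SD set to 1:

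- variance of change = 1 + k² − 2ρk
- residual variance under ANCOVA = 1 − ρ²
- ratio = (1 − ρ²) / (1 + k² − 2ρk)
- extra participants for the t-test = 1/ratio − 1

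Example with k = 1 and ρ = 0.5: ratio = 0.75/1 = 0.75, and 1/0.75 − 1 = 33%.

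| k | ρ 0.4 | 0.5 | 0.6 | 0.7 | 0.8 |
|---|---|---|---|---|---|
| 1.0 | 43% | 33% | 25% | 18% | 11% |
| 0.9 | 30% | 21% | 14% | 8% | 3% |
| 0.8 | 19% | 12% | 6% | 2% | 0% |

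A simulation with 50 per arm and 20,000 runs, at ρ = 0.4/0.6/0.8, gave 43/24/11% (k = 1), 28/13/2% (k = 0.9) and 18/5/−1% (k = 0.8). In the last case the true slope is 0.8/0.8 = 1, so the change score is already optimal and estimating the slope costs a little.

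**2. Power.** If the t-test has 80% power, ANCOVA power = Φ(2.802/√ratio − 1.960), where 2.802 = 1.960 + 0.842. For ρ from 0.4 to 0.8:

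- k = 1: 92% to 84%
- k = 0.9: 89% to 81%
- k = 0.8: 86% to 80%

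A separate simulation (4,000 trials, 50 per arm, k = 1) gave a type I error of about 4.8% for both methods. For a 0.4 SD effect, power was 51% (t-test) against 64% (ANCOVA) at ρ = 0.5, and 73% against 79% at ρ = 0.7.

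**3. Chance baseline imbalance.** The change-score difference moves by (ρ/k − 1) per point of imbalance: −0.60 to −0.20 (k = 1), −0.56 to −0.11 (k = 0.9) and −0.50 to 0 (k = 0.8). A 3-point imbalance therefore shifts it by 1.8 to 0.6, 1.7 to 0.3 or 1.5 to 0 points. In scale-free terms, a 0.2 SD imbalance at k = 1 and ρ = 0.5 shifts it by (1 − 0.5) × 0.2 = 0.10 SD.

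**4. Omitted strata.** If balanced strata explain a share R² of the variance of change, the t-test's standard error is too large and the true type I error is 2[1 − Φ(1.96/√(1 − R²))]. For R² = 0.05, 0.10 and 0.20 this is 4.4%, 3.9% and 2.8%. Because the strata are unnamed, these R² values are hypothetical.

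**5. Within-arm tests.** Assume no treatment effect, the same true change in both arms, SD of change 15 and 50 per arm. Let p be the power of one paired t-test. Exactly one arm is significant with probability 2p(1 − p), and the app arm alone with p(1 − p).

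| True change in both arms | p | Exactly one arm | App arm only |
|---|---|---|---|
| 2 | 0.152 | 26% | 12.9% |
| 4 | 0.456 | 50% | 24.8% |
| 6 | 0.792 | 33% | 16.5% |
| 8 | 0.959 | 8% | 4.0% |
| 10 | 0.996 | 1% | 0.4% |

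For two independent tests of equal power, 50% is the maximum of 2p(1 − p).

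**The case against.** The strongest reply is that nothing here is invalid. The confirmatory comparison is already adjusted, the t-test holds its level under randomisation, and the documents claim no power for secondary endpoints. That stands, and it limits the matter to efficiency and consistency. It does not justify leaving available precision unused.

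The gain may also be nil, as the corner at k = 0.8 and ρ = 0.8 shows. Nor do the ranges bound the effect from above: at k = 1.2 the same formula gives 76% (ρ = 0.4) to 44% (ρ = 0.8). The THI entry limit bears only indirectly on the subscales and says nothing about TFI, VAS, BDI or BAI, and the point-scale illustrations are not tied to one instrument. These are fair limits on the figures, which illustrate the effect but do not estimate it for this trial.

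A mixed model with baseline as a response and a common baseline mean would adjust without a named covariate. The plan only permits such models and specifies none, so this does not fill the gap.

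That the t-tests are on change is inferred from how the variables are defined. If they were on raw week-6 scores, baseline and strata would still be missing, and the extra sample would be 1/(1 − ρ²) − 1: 1/0.84 − 1 = 19% at ρ = 0.4, and 1/0.36 − 1 = 178% at ρ = 0.8.

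Finally, the plan nowhere says efficacy will be inferred from paired tests. Labelling them is therefore a clarification and would carry little weight alone.

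**Conclusion.** The point holds. The only definite between-arm method for the secondary variables omits the covariates that the primary model uses, and nothing else in the documents supplies them. The primary result is not affected and type I error is not inflated. The avoidable cost is roughly 0% to 43% in sample-size terms for ρ of 0.4 to 0.8 and an SD ratio of 0.8 to 1, with 1:1 allocation assumed. There is also avoidable sensitivity to baseline imbalance, and some conservatism if the strata are prognostic. The change should be made because the covariates are already to hand, though the plan does not fail without it. The within-arm label is a minor addition.

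**What to change.** For each secondary variable, replace the two-sample t-test as the main between-group analysis with an ANCOVA of change at week 6, adjusted for that variable's own baseline and the stratification factors of the primary model. Report the adjusted difference with its 95% CI. The t-test may stay as a supportive analysis.

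If a longitudinal analysis is preferred, specify a linear mixed model over weeks 2, 4 and 6 with arm, visit, arm-by-visit and the same covariates, and take the week-6 contrast from it. Fix the choice between the two in advance.

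Name the stratification factors, and say how the normality rule and the LOCF rule apply to the chosen model. State that within-arm changes and their paired tests are descriptive and are not used as evidence of efficacy.

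Adjusted subscale differences will still not sum exactly to the adjusted total, because each model uses its own baseline. The aim is a consistent method, not additivity.

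The cost is SAP wording and minor programming. No new data are needed: each scale's baseline is already summarised and the factors are already in the primary model.

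### Safety is a stated aim, but the tests named for vital signs, physical and laboratory findings are all before-after tests, and no between-arm safety comparison is stated

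*Combined protocol and SAP*

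**What the plan says.** The Objectives and Design sections of the combined protocol and SAP both name safety, next to efficacy, as something the trial is to evaluate. The Design section sets up a randomised control group that receives educational materials.

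The whole safety analysis is one sentence in the Statistical Analysis Plan. Its first part reads "Safety evaluation includes reporting adverse events, assessing vital signs using paired t-tests or Wilcoxon signed-rank tests", and it continues "analyzing physical and laboratory findings with paired t-tests for continuous variables and McNemar's test for categorical variables". Elsewhere in that section a general rule states that "categorical variables are summarized by frequency and percentage"; the rule does not mention arms.

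For efficacy the same section is explicit about comparing arms. The primary variable is "analyzed using ANCOVA to compare groups while adjusting for baseline THI" and the stratification factors. Each secondary variable has "paired t-tests or Wilcoxon signed-rank tests used within groups and two-sample t-tests between groups".

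On populations, "the Safety Analysis Set includes all participants who have used the medical device at least once".

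**The concern.** In a randomised trial, the control arm is what separates an effect of the app from change that would have occurred anyway. The paired t-test, the Wilcoxon signed-rank test and McNemar's test each ask whether values moved from baseline. None asks whether they moved more in one arm than in the other. The plan draws the distinction between within-group and between-group analysis for secondary efficacy and does not draw it for safety.

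At stake is how the safety aim is answered. A significant before-after change in the app arm could be background drift shared with controls. An app effect offset by drift in the other direction would not show in the app-arm test. Either way, the report would give no estimate of the app's effect on a safety measure and no interval showing how large an effect remains compatible with the data.

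**Working it through.** The documents give no sample size, allocation ratio, event rate or safety figure, so there is no stated number to reproduce. The check is a classification of the named methods, followed by what each one estimates.

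**Step 1. Classify every named analysis** (all from the Statistical Analysis Plan).

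- Primary efficacy, THI total: ANCOVA, between arms.
- Secondary efficacy, five entries as listed ("Secondary efficacy variables include changes in THI subscales, Tinnitus Functional Index (TFI), Visual Analog Scale (VAS) for negative emotions and thoughts", then BDI and BAI): two-sample t-test between arms, plus paired tests within arms.
- Vital signs: paired t or Wilcoxon signed-rank, before-after only.
- Physical findings: paired t or McNemar, before-after only.
- Laboratory findings: paired t or McNemar, before-after only.
- Adverse events: to be reported; no test and no by-arm difference named.

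Efficacy: 1 + 5 = 6 variables, 6 of 6 with a between-arm method. Safety: 4 items, 0 of 4 with one; 3 of the 4 have before-after tests only.

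**Step 2. What each analysis targets.** Let m be the mean background change, d the mean effect of the app on that change, and w the share of participants in the app arm.

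- Paired test in the app arm: m + d.
- Paired test in the control arm: m.
- Paired test on pooled data: w(m + d) + (1 - w)m = m + wd.
- Between-arm difference: (m + d) - m = d.

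These identities hold at any sample size. Only the last line isolates d.

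**Step 3. Read the safety sentence both ways.** It says neither per arm nor pooled.

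- *Per arm.* The adjoining secondary-efficacy sentence uses paired tests within groups, so this is the more natural reading. If d = 0 and m is not 0, both arms target m, and the shared drift can be recognised as such. If m = -d, the app arm targets 0 and the control arm targets -d, so the contrast is there to be seen. What is missing is d itself with a confidence interval.
- *Pooled.* The target is m + wd, and the arms cannot be told apart. How much of d survives depends on w, which the documents do not give, and they do not state that pooling is planned, so no figure is put on it here.

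**Step 4. Why two p-values side by side do not replace the difference.** Suppose the true change is the same in both arms and each within-arm test has the same power p (independent arms; p is assumed, not taken from the documents). The chance that exactly one arm is significant is 2p(1 - p):

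- p = 0.05: 2 × 0.05 × 0.95 = 0.095
- p = 0.20: 2 × 0.20 × 0.80 = 0.32
- p = 0.50: 2 × 0.50 × 0.50 = 0.50
- p = 0.80: 2 × 0.80 × 0.20 = 0.32
- p = 0.90: 2 × 0.90 × 0.10 = 0.18

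A direct two-sided between-arm test at the plan's 5% level would err 5% of the time. The plan states no rule for comparing p-values across arms. The figures show only what would follow if a reader did so for want of a difference.

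**The case against.** The strongest reply has four parts.

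- **The control arm is not ignored.** On the per-arm reading it is tested too, and its change stands beside that of the app arm. This stands. A reader might infer that the safety analysis makes no use of randomisation, but that is true only if the data are pooled, which the text does not say. If means and standard deviations of change are tabulated per arm, a reader could even derive a crude difference for continuous measures, though the plan does not commit to that display.
- **Descriptive safety reporting is normal.** This is a superiority trial on THI, with no safety hypothesis, margin or success criterion. This also stands, and it is why formal safety tests are not being asked for. But the plan is not purely descriptive: it names significance tests for three of the four safety items, and those tests do not target the app effect.
- **Adverse events will be tabulated by arm anyway.** In a two-arm trial that is the ordinary reading, and the general rule on frequencies and percentages supports a table. A reader might infer that adverse events will be lumped together; the documents do not support that. What is unstated is a between-arm difference.
- **The plan is very condensed, and its safety list is introduced as non-exhaustive.** Silence in a one-sentence safety plan is weaker evidence of a deliberate choice than silence in a full SAP. That limits confidence. Yet equally brief wording was enough to state between-arm methods for efficacy, and no other section supplies one for safety.

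**Conclusion.** The point holds as a gap in the safety analysis, with medium confidence. The named tests for vital signs, physical and laboratory findings are all before-after, and no between-arm safety comparison is stated for these or for adverse events. On the per-arm reading, the plan shows the two components but never estimates their difference; on the pooled reading, it does not separate the arms.

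The consequence is low to moderate. The primary ANCOVA is untouched and no stated success criterion depends on safety. No error rate or bias is claimed for this trial, because the documents give no figures from which to compute one.

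One further inference should be resisted. Both the Safety Analysis Set and the efficacy population ("the Full Analysis (FA) set includes all participants who have used the medical device at least once", with an efficacy evaluation also required) are defined by use of the device, while controls receive educational materials. A reader might conclude that controls are excluded from safety. The wording is unclear on this but does not establish it. It is a separate question that also bears on the primary population, and it adds no weight to the present point. It matters here only because a between-arm comparison needs the controls.

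**What to change.** Amend the safety paragraph of the Statistical Analysis Plan as follows.

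- Report change in vital signs, physical and laboratory findings by arm, with the between-arm difference and its 95% confidence interval, adjusted for baseline where the measure is continuous.
- Keep the paired t, Wilcoxon signed-rank and McNemar results, run per arm and labelled descriptive.
- Tabulate adverse events by arm as frequency and percentage, with a risk difference and 95% confidence interval.
- State that no formal hypothesis test is planned for each safety variable.

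Two conditions must be met first. The Safety Analysis Set must be worded so that it clearly includes control participants, and the same safety data must be collected in both arms, which the documents do not confirm. If both hold, the cost is a few lines of SAP text and a few extra tables, with no new trial procedures and no change to the primary analysis method.
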